Over 5.1 million Americans suffer from heart failure (HF), with over \$32 billion expended annually.¹ Although survival from HF has improved, a diagnosis of HF is similar to some forms of cancer, with 50% of patients dying within 5 years of diagnosis.¹ Ventricular assist devices (VADs) have improved survival in patients with advanced HF.² Over 17,000 patients with advanced HF have received VADs in the last decade, and implantation rates are expected to increase with newer generation devices.³ VADs may be used as “destination” (e.g., permanent) therapy or as a “bridge to transplant.” Patients on Destination Therapy will remain on the VAD for the rest of their lives. Bridge to Transplant patients will remain on the VAD until time of heart transplant. VAD devices are surgically implanted into the apex of the left ventricle of the heart and are connected to the aorta, providing circulatory support to the patient. A driveline passes from the device through the skin, connecting to a system controller that in turn is connected to external power. A frequent and often deadly complication after VAD implantation is driveline infection. Infection can cause pump failure from thrombosis, which requires surgical pump exchange if the patient survives the event.⁴

Immediately prior, and around the time of VAD implantation, patients and their caregivers are educated about VAD self-management. However, patients are often critically ill during this hospitalization, and caregivers (often family) are under emotional duress; thus skill retention with this traditional education may be lacking. After discharge, patients and caregivers are required to engage in significant daily VAD self-management including: driveline exit site dressing changes; performing controller self-tests; changing power sources; troubleshooting emergent VAD-related malfunction; and recognizing VAD-specific signs and symptoms requiring immediate contact with the VAD team. With insufficient VAD-related knowledge and improper VAD self-management, these patients can die from **preventable** complications including driveline infections.⁵

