Two VAD nurses will perform usual training only, which is the current standard of care. First, patients and caregivers watch a video produced by the VAD manufacturer. Subsequently, the VAD nurse trains the patient and caregiver per usual routine with a non-implanted VAD. These meetings occur 1 to 3 times depending upon patient and caregiver availability and are not standardized. During the VAD implantation hospitalization, the caregiver completes a written examination to assess knowledge. The VAD nurse observes patient and caregiver completion of skills and deems competence based only on observation. Historically, patient and caregivers are variably able to participate in training sessions. If the patient is too ill to participate in training before VAD implantation, only the caregiver completes training and the patient is trained during the hospital stay for implantation at which point they are significantly clinically improved.

Three VAD nurses will administer SBML training. The SBML training group will first 1) watch the VAD video, then 2) participate in pre-intervention assessments using the simulator for a) driveline exit site sterile dressing changes; b) performing controller self-tests; c) changing power sources; d) troubleshooting emergent VAD-related malfunction; and e) recognizing specific signs and symptoms requiring immediate contact with the VAD team. The patient and caregiver

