then will participate in deliberate practice on the simulator with feedback from the instructor. We anticipate 2 training sessions of 1-2 hours each to become proficient in these skills. After training, the patient and caregiver complete a post-intervention assessment on the simulator using the checklists. At the end of training, the patient and caregiver will complete the written examination to assess knowledge and will be required to meet or exceed the MPS on the checklists and written examination. If they fail to meet the MPS, they will receive additional training until they meet the MPS. If the patient is ever too ill, only the caregiver will participate in the training and the patient will be trained during the hospital stay for implantation. Both training groups. After training, we will ask participants to rate their educational experience and their confidence in performing each of the 5 VAD self-management tasks [via a questionnaire adapted from our previous work. All participants will demonstrate the five skill domains on the actual VAD patient during the implantation hospitalization (Time 0), and at one and three months after training to assess skill retention. Assessments will be performed during office visits, as patients are seen at least monthly after VAD implantation, or re-hospitalizations. If caregivers cannot attend, assessments will be performed via internet video. We anticipate the majority of enrolled patients will have internet access; alternatively, we will arrange sessions at their local library.

A trained VAD nurse (who is not assigned to teach the curriculum) will perform all patient and caregiver assessments using the checklist. In the absence of this nurse, the PI or a Co-I will perform assessments; we expect this to be rare. The trained VAD nurse, the PI and COCo-I will be blind to the intervention received by the patient and caregiver. A random sample of 25% of all assessments will be double scored by both the VAD nurse and PI or Co-I to assess inter-rater reliability.

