After VAD implant, patients are managed by the VAD team with frequent office visits. Complications and re-hospitalizations are documented in outpatient and/or inpatient medical records. Patients admitted to a local hospital are typically transferred to NMH for care. If patient is admitted to another hospital, they are customarily transferred to NMH to manage the VAD. We believe we will be able to capture all data about driveline infections and re-hospitalizations prospectively.

NMH's infection prevention department also tracks *all* VAD related driveline infections using definitions in the INTERMACS database.³⁷ We will assess patient factors at time of infection and during re-hospitalization to evaluate differences between the SBML and usual VAD training groups such as age, sex, body mass index, and the Charlson comorbidity codes. The Charlson score is based on 19 chronic disease comorbidities derived from the International Classification of Disease Revision 9 (ICD-9) codes and predicts one-year mortality for hospitalized patients. We can obtain all admission ICD-9 codes from our Enterprise Data Warehouse⁹³ which also convert ICD-10 codes to their corresponding ICD-9. We will obtain additional data using the INTERMACS database (includes all NMH patients), which provides type of VAD, VAD indication (DT vs. BTT), and infection and re-hospitalization rates.

DATA AND SPECIMEN MANAGEMENT:

Primary outcome measures are comparisons of VAD-care checklist assessments on the patient and written examination scores between SBML and usual training groups. Secondary outcome measures include self-management skill decay in the five domains from 0 to 3 months and comparisons of post-training questionnaires between groups.

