We will estimate checklist score inter-rater reliability using the Kappa (κ) coefficient^{84,87}. Our prior work shows the difference between traditional training and SBML interventions is approximately 33%; traditionally trained simulated skill checklist performance averages 61.47% (SD=24.48) items correct while SBML training performance averages 94.88% (SD=6.63).^{9,48,51,53,88} We anticipate the usual training group in our study will perform similarly to the traditionally trained healthcare providers in our prior studies. Sample sizes of 65 in each group (total =130) achieve 82% power to detect at least 10% difference between the usual group and the SBML training group assuming a mean checklist score of 85% in usual group (SD=25) and 95% in the SBML training group (SD=10) with a significance level of 0.05 using a two-sided t-test. As the distribution of % items correct is likely to be non-parametric, adding 15% requires 75 in each group.⁸⁹ Therefore, our study will be overpowered to detect a 33% difference. We will compare checklist scores on actual patient assessments between usual care and SBML-trained groups using the independent t-test or Wilcoxon rank sum test (if data are non-parametric). We will compare age, sex, race/ethnicity, level of education, employment status, zip code, type of VAD, and VAD indication (DT vs. BTT) between groups using either Chi Square test or independent t-tests. If there is a difference between the randomized groups in any of these variables at the level of $p \leq 0.1$, we will use multiple linear regression or multiple quantile regression (for non-parametric data) to assess these variables independently on scores between the two groups. We will measure skills decay between groups using an analysis of variance (ANOVA) or a non-parametric analysis of variance at 0, 1 and 3-month assessments. Questionnaire results will be compared between groups using Chi-Square, independent t-test, or Wilcoxon rank sum where appropriate.

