We will compare driveline infections and re-hospitalization rates at one and three months after VAD implantation between the SBML and the usual training groups using the Chi Square test, recognizing that we may be underpowered for this exploratory aim due to the short study time frame. We will compare age, sex, race/ethnicity, level of education, employment status, zip code, type of VAD, VAD indication (DT vs. BTT), and Charlson scores between groups using either the Chi Square test or independent t-tests. If there is a difference between the randomized groups in any of these variables at the level of $p \leq 0.1$, we will perform multiple logistic regression to control for these independent variables between groups. If some patients have more than infection, we will use random effects modeling to account for clustering by patient.

The study PIs, co-investigators, as needed, VAD nurse, and Research Coordinator (RC) will have access to individually identifiable data. Otherwise, a unique identification code will be assigned to each enrolled patient, and all of the data entered into the system for that patient will be identified by this code rather than by name.

Socio-demographic and medical records data will be collected by INTERMACS and exported to a secure web server at Northwestern University. Socio-demographic data collected from VAD caregivers and checklist of VAD self-maintenance tasks-performance data will be collected on paper but will be de-identified using a unique identifier for each patient or caregiver. This data will be stored on a Northwestern Server that is password protected and encrypted. All data will be collected specifically for research purposes.

WITHDRAWAL OF PARTICIPANTS:

Participants are free to withdraw from the study at anytime without consequences.

RISKS TO PARTICIPANTS:

There are two potential risks of participating in this study for patients:

1. Potential for breach of patient confidentiality. This is a very serious potential risk to patients, but safety measures, as described above, have been put into place and are monitored by the Northwestern University IRB.

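### The retention analysis names an ANOVA at 0, 1 and 3 months without its type or a rule for missed assessments; a mixed model on all observed scores is better under any reading

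*Combined protocol and SAP*

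**What the plan says.** Under OBJECTIVES, Hypothesis 1b is that skills are better retained at one and three months after the simulation-based mastery learning (SBML) training than after usual training. DATA AND SPECIMEN MANAGEMENT makes this a secondary outcome: "Secondary outcome measures include self-management skill decay in the five domains from 0 to 3 months". The analysis is a single sentence in the same section, which will measure "skills decay between groups using an analysis of variance (ANOVA) or a non-parametric analysis of variance at 0, 1 and 3-month assessments".

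PROCEDURES INVOLVED has each participant assessed "during the implantation hospitalization (Time 0), and at one and three months after training to assess skill retention". It also describes arrangements that limit missed assessments: "Assessments will be performed during office visits, as patients are seen at least monthly after VAD implantation, or re-hospitalizations", and "If caregivers cannot attend, assessments will be performed via internet video", with a local library session where there is no internet access.

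WITHDRAWAL OF PARTICIPANTS says only: "Participants are free to withdraw from the study at anytime without consequences". The text available for review gives no expected rate of missed assessments and no rule for analysing incomplete participants. The 15% added to the sample size is for non-normal scores, not attrition. A random effects model is named for patients with more than one infection, but not for repeated skill scores.

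**The concern.** Decay is a change within a person, and the scores are three repeated measurements on the same people. The method has to link a person's scores and has to do something when one is absent. The sentence settles neither.

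- **Repeated-measures ANOVA or a Friedman-type test, in classical form:** needs all three scores, so one missed visit removes the person.
- **A separate analysis at each visit:** uses every score, but compares whoever attended. If attendance depends on how well people did at Time 0, the arms are no longer comparable at months 1 and 3.
- **A factorial ANOVA of arm by visit on all scores:** treats one person's three scores as independent, so its standard errors are wrong.

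Hypothesis 1b is at stake. The plan assumes lower and more variable scores in the usual arm, so any link between low scores and missed visits would thin the two arms unequally.

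**Working it through.** **The plan's own figures.** None is given for retention. The nearest is the sample-size statement: 65 per group, means 85 and 95, SDs 25 and 10, two-sided 0.05, 82% power. The standard error is √(625/65 + 100/65) = 3.34, and 10/3.34 = 2.99. The unequal-variance t-test then has 84.1% power; allowing a rank-test efficiency of 0.955 gives 82.4%. The stated 82% is therefore not disputed. 65 × 1.15 = 74.75, which gives the plan's 75. None of that increase is for attrition.

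**People left for a three-visit analysis.** Assume (not from the documents) that Time 0 is always scored and that a share *m* misses each follow-up visit independently. Complete cases are (1−m)². The share of collected scores discarded is 1 − 3(1−m)²/[1 + 2(1−m)]. Counts are for 75 per group.

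| m | Complete | Complete cases per group | Scored at each follow-up | Collected scores discarded |
|---|---|---|---|---|
| 5% | 0.95² = 90% | 68 | 71 | 6.6% |
| 10% | 0.90² = 81% | 61 | 67.5 | 13.2% |
| 20% | 0.80² = 64% | 48 | 60 | 26.2% |
| 30% | 0.70² = 49% | 37 | 52.5 | 38.8% |

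If instead the same 15% miss both follow-ups, 85% of people remain and the loss is 0.15/(1 + 2 × 0.85) = 5.6% of collected scores.

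**Bias, by mechanism.** This is a large-sample simulation with 200,000 per arm. The SDs of 25 and 10 and the Time 0 means of 85 and 95 are the plan's. The rest is assumed: means at 0, 1 and 3 months of 85, 80, 75 (usual) and 95, 92, 90 (SBML), within-person correlation 0.6, and scores not capped at 100. The true month-3 difference is 90 − 75 = 15. The true difference in decay is 10 − 5 = 5. Misses are either 15% at random, or follow logit(p) = −2.0 − 0.5 × (score − 90)/10. The score is either that at Time 0 (about 20% missed in usual, 10% in SBML) or the unseen current one (24–28% and 12–13%).

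| Misses depend on | Contrast | True | Complete-case | Per-visit | Likelihood model |
|---|---|---|---|---|---|
| Nothing | Month-3 difference | 15 | 14.92 | 14.97 | 14.99 |
| Nothing | Difference in decay | 5 | 4.99 | 4.95 | 4.98 |
| Time 0 score | Month-3 difference | 15 | 10.26 | 12.14 | 14.95 |
| Time 0 score | Difference in decay | 5 | 8.10 | 2.18 | 4.99 |
| Unseen current score | Month-3 difference | 15 | 6.53 | 8.75 | 10.96 |
| Unseen current score | Difference in decay | 5 | 2.77 | −1.19 | 1.01 |

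Regression to the mean explains the opposite directions in the Time 0 rows. Complete cases in the usual arm start at 93.84 instead of 85 and fall to 80.31, a drop of 13.53 against a true 10. In the SBML arm they go from 96.01 to 90.57, a drop of 5.44 against a true 5. The excess decay is 13.53 − 5.44 = 8.09, while the month-3 gap closes.

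**A second set of assumptions** has a true month-3 difference of 11, correlation 0.4 to 0.6, and 10–20% missed at a Time 0 score of 90. The log-odds of missing rise by 0.7 to 1.0 per 25 points lower. Complete-case analysis gives 5.8–9.6, per-visit 8.0–10.3 and likelihood 10.9–11.1. Capping scores at 100 reduces the bias but does not remove it: complete-case gives 9.2–11.9 against about 13.0. With misses unrelated to score there is no bias, but the complete-case variance of the month-3 difference is 14–35% larger than under the likelihood model.

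**The case against.** The strongest reply is that the plan never says it will use complete cases. A reader might infer that it will, because the data are repeated, but no sentence says repeated-measures, Friedman or all three visits. The phrase about comparing groups in fact fits a Friedman test poorly, since that test has no between-arm factor. A per-visit or factorial analysis fits the wording and uses every score. This stands, so complete-case loss is only one of the possible consequences. It does not rescue the plan, because the alternatives have the faults shown above.

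A reader might also infer that a very ill population will lose much of its data. The documents do not support that. The statement that "patients are often critically ill during this hospitalization" concerns the implantation stay. Of patients too ill to train beforehand, the protocol says "the patient is trained during the hospital stay for implantation at which point they are significantly clinically improved". Half of those assessed are caregivers. The video provision is a safeguard against missing data, not evidence of it, and the right to withdraw predicts no rate.

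The missingness assumed in the simulations is steep at its upper end. With 20% missed at a score of 90 and a log-odds slope of 1.0 per 25 points, a person scoring 60 has odds 0.25 × e^1.2 = 0.83, or 45% missed per visit. Nothing in the documents supports or excludes this.

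Finally, the mixed model is no cure for misses driven by unseen scores (1.01 against a true 5). That also stands, and is why a sensitivity analysis belongs with it.

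**Conclusion.** The point holds as a choice of method that should be changed, for a secondary outcome that carries a named hypothesis. The type of ANOVA and the handling of missed assessments are unstated, and every reading is inferior to a likelihood-based mixed model once visits are missed.

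The size is conditional. Over assumed miss rates of 5% to 30% per follow-up visit, a three-visit analysis keeps 90% down to 49% of people. A lower figure, such as 0.8³ = 51% at a 20% miss rate, needs Time 0 to be missed as often as the follow-ups.

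One direction of bias should not be claimed. Misses unrelated to score cost precision only. Misses that depend on the Time 0 score make complete-case analysis understate the month-3 difference and overstate the difference in decay, and decay is what the plan's sentence is about. Misses that depend on unseen scores shrink both in the simulation. The bias figures rest on assumed means, correlations and missingness and are illustrations. The primary comparison is a separate t-test or rank-sum test and is not in question here.

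**What to change.** Replace the ANOVA sentence with a likelihood-based linear mixed model fitted to all observed scores at 0, 1 and 3 months:

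- fixed effects for arm, visit and arm by visit;
- effects for person and for patient-caregiver pair;
- arm-specific variances, since the plan itself assumes SDs of 25 and 10;
- robust or bootstrap standard errors, because scores pile up near 100%.

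Take from it the arm differences at months 1 and 3 and the arm difference in change from Time 0. Report the number of missing assessments, and the reasons, by arm and visit. Add a sensitivity analysis in which missed scores are allowed to be worse than the model predicts, by amounts that may differ between arms.

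The cost is analysis wording and modest programming; no further skill assessments are needed, and the plan already uses random effects for repeat infections. The downside is reliance on missing-at-random and on approximate normality. The model does not remove bias from misses driven by unseen scores; the sensitivity analysis shows only how far the conclusion depends on that.

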Each individual enrolled will participate in the study for approximately 3 months. We anticipate enrollment of study subjects will take approximately 15 months. We hope to complete all analyses 2 two years.

STUDY ENDPOINTS:

The primary study endpoints are we have enough patients enrolled to compare VAD-care SBML training and usual training groups.

PROCEDURES INVOLVED:

Approximately 60 advanced HF patients undergo VAD implantation at NMH yearly. During our 15-month study period, up to 75 participating patients and 75 caregivers will be eligible to receive either the SBML VAD self-management curriculum or usual VAD training. Eligible patients will be about to undergo VAD implantation at NMH, age >18, and English-speaking. Eligible caregivers will be identified by a VAD implantation patient, age >18, and English-speaking. Advanced HF patients who are scheduled for VAD implantation will receive information about the study at their pre-implantation clinic visits or during hospitalization. Consenting patients will be asked to provide the name and contact information of their primary caregiver; we will contact the caregivers to explain the study and assess their interest. Patients and caregivers must both agree to participate in the study to be enrolled. All Patient and caregiver VAD self-management training begins before implantation and continues up to the hospitalization for VAD placement.

Study randomization will be conducted via random number generator. After randomization, demographic data including age, sex, race/ethnicity, and socioeconomic (SES) factors such as zip code, highest level of education, and employment status will be collected from patients and caregivers.

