The research settings for recruitment and enrollment of patients is Northwestern Memorial Hospital, Northwestern University, Chicago, IL. Patients will be recruited either at the medical center (while the patient is hospitalized) or during a clinic visit. The co-investigators, who provide care to patients with ventricular assist devices (VADs) will share information about the study with patients. If the patient's caregiver is not present at this time, we will contact them via phone or via mailed brochure to explain the study and then consent in person when they arrive for their VAD training.

The PI, CO-I or VAD nurse, will further explain the study to patients and caregivers, encourage them to ask questions, and obtain written informed consent. Patients and caregivers will be informed that if they decline to participate in the study, it will not prejudice current patient care, and they may discontinue participation at any time during the study with no adverse impact to their treatment or care. Verbal and written information provided to potential participants during informed consent will include the following: the purpose of the study, the nature of the questions asked during interviews, the method and frequency of skills assessment completion, the length of time required, the voluntary nature of participation in the study, the ability to not respond or participate in any parts if requested, the freedom to withdraw from the study at any time without consequences, the potential risks and benefits of study participation,

and the confidentiality of information gathered. A brochure with an overview of the study will also be provided. Patients will also be shown their study results, if desired. Patients who are enrolled in INTERMACS will also be informed that INTERMACS will securely transmit data to Northwestern, as well, which is already done for other studies. We will also incorporate language into their consent form that includes a statement about INTERMACS protected health information being transmitted securely to Northwestern. Patients who agree to participate in the study will sign an informed consent form. A copy of the signed consent form will be given to the patient, a second copy of the consent form will be placed in the patient's medical record, and the original copy will be kept and filed by the RC

NUMBER OF LOCAL PARTICIPANTS:

We expect to recruit 75 patients and 75 caregivers. One caregiver will be identified by each patient subject.

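### The adjusted Aim 2 model for driveline infection is ordinary logistic regression in about 75 patients, with no provision for an arm or covariate level that has no infections

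*Combined protocol and SAP*

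**What the plan says.** The Aim 2 analysis is in the protocol section DATA AND SPECIMEN MANAGEMENT: "We will compare driveline infections and re-hospitalization rates at one and three months after VAD implantation", by Chi Square test. Nine baseline variables are then compared between arms. Two are numerical (age and Charlson score). Seven are categorical: sex, device type, indication, race/ethnicity, education, employment and zip code. The adjusted model is conditional: "If there is a difference between the randomized groups in any of these variables" at p ≤ 0.1, "we will perform multiple logistic regression to control for these independent variables between groups".

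On size, NUMBER OF LOCAL PARTICIPANTS states "We expect to recruit 75 patients and 75 caregivers". PROCEDURES INVOLVED gives the source: "Approximately 60 advanced HF patients undergo VAD implantation at NMH yearly", and "During our 15-month study period, up to 75 participating patients and 75 caregivers will be eligible". The allocation ratio is not given; the text says only "Study randomization will be conducted via random number generator".

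The plan calls Aim 2 exploratory and concedes that it may lack power. It gives no infection rate, no limit on the number of covariates, no rule for merging categories and no method for empty cells. Its random-effects provision covers patients with repeat infections, which is a different problem.

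**The concern.** Infection is counted in patients, so Aim 2 rests on about 75 observations at one and three months. A maximum-likelihood log odds ratio is infinite when one arm has no events. The same happens to the coefficient for a level of a categorical covariate in which nobody has an event. Software may then stop, drop patients, or print an extreme odds ratio with a meaningless standard error. With a handful of infections and several multi-level candidates, this is a realistic outcome.

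At stake is whether the adjusted infection result, the one closest to clinical benefit, can be reported. An empty arm is also more likely if training works, because the trained arm then has fewer infections. This concern is separate from choosing covariates by a significance test.

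**Working it through.** **Number of patients.** 60 per year × 15/12 years = 75, which reproduces the plan's figure. With 1:1 allocation (assumed) the arms are 37 and 38. The Aim 1 statement "adding 15% requires 75 in each group" fits 75 + 75 = 150 patients and caregivers counted together. It cannot mean 75 patients per arm, because only 75 patients are expected.

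**Given the total number of infections (no rate needed).** With three infections and no effect, the chance that all fall in one arm is [C(37,3) + C(38,3)] / C(75,3) = (7,770 + 8,436) / 67,525 = 24%. The same formula gives 49% for two infections, 12% for four and 5% for five.

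**An arm with no infections, by assumed risk.** With p1 for the 37 usual-training patients and p2 for the 38 trained patients:

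P = (1−p1)^37 + (1−p2)^38 − (1−p1)^37 × (1−p2)^38

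- 5%, no effect: 0.1499 + 0.1424 − 0.0213 = 0.271.
- 5% against 2.5%: 0.1499 + 0.3821 − 0.0573 = 0.475.

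**A covariate level of 10 patients with no infections.** (1−p)^10 is 60% at 5% risk, 35% at 10%, 20% at 15% and 11% at 20%.

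**The plan's own rule, simulated.** There were 1,200 trials of 37 against 38 patients per setting. Eight of the nine covariates were tested at p ≤ 0.1, and only those that differed entered the model. Infinite coefficients were detected by a linear-programming check for separation; a trial with no infections also counts. Assumed frequencies (%):

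- sex 75/25
- race/ethnicity 60/25/10/5
- education 10/30/35/25
- employment 30/30/40
- device type 60/40
- indication 50/50

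Age and Charlson score were normal, and no covariate was related to infection. Zip code was left out.

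The model was triggered in 55–59% of trials, as expected from eight tests: 1 − 0.9^8 = 57%. Each simulated percentage rests on roughly 660 to 710 triggered trials, so its standard error is at most about 2 points.

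| Usual-arm risk | Expected infections, no effect | Empty arm: no effect / risk halved | Some coefficient infinite when model is run: no effect / risk halved |
|---|---|---|---|
| 2% | 1.5 | 72% / 83% | 90% / 93% |
| 5% | 3.8 | 27% / 47% | 59% / 74% |
| 10% | 7.5 | 4% / 16% | 35% / 45% |
| 15% | 11.3 | 0.5% / 5% | 21% / 30% |
| 20% | 15 | <0.1% / 2% | 17% / 24% |
| 30% | 22.5 | <0.1% / 0.2% | 9% / 13% |

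Swapping which arm has 38 patients changes the risk-halved figures for an empty arm to 48%, 17% and 6% at 5%, 10% and 15%.

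**Over all trials, triggered or not (no effect).** 0.567 × 0.588 = 33% at 5% risk, 0.566 × 0.351 = 20% at 10%, 0.562 × 0.206 = 12% at 15% and 0.552 × 0.170 = 9% at 20%.

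**Which coefficient fails.** An empty arm always makes the fit infinite, so the remainder is failure with infections in both arms. At 10% risk with no effect, 35.1% of triggered fits failed and 3.7% had an empty arm. The other 31.4 points are therefore mainly covariate coefficients.

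**The case against.** The strongest reply is that little is lost. Aim 2 is exploratory, its low power is admitted, it is not among the listed primary or secondary outcomes, and the unadjusted Chi Square comparison does not depend on the adjusted model. The model may never be run. When it fails at moderate rates, the failure is usually in a covariate level, and the training odds ratio generally stays finite. The infection rate and category frequencies are assumptions. All of this stands, and it limits the severity. It does not answer the point: admitting low power warns of a wide interval, not of an estimate that does not exist.

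Three stronger readings are tempting, and the documents support none of them.

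- **A reader might infer that the adjusted training effect would often be inestimable.** That holds only at risks of about 5% or below, or at somewhat higher risks if training is very effective. Forcing indication and an assumed four-level education factor into every trial gives infinite coefficients in about 97%, 89%, 48% and 23% of trials at 3%, 5%, 10% and 15% risk. That is not the plan's analysis, which runs only after an imbalance.
- **A reader might extend the point to all of Aim 2.** All-cause re-hospitalization may have many more events. No rate is given either way.
- **A reader might doubt the Chi Square test.** Its exact level at 37 against 38 is 0.017, 0.038, 0.051 and 0.051 at 3%, 5%, 10% and 15% risk, so it does not materially exceed 5%.

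**Conclusion.** The point holds for driveline infection, at low severity. If the three-month risk is about 10% or less, the planned model, when triggered, has a substantial chance of at least one infinite coefficient. At 15–20% this is occasional, and at 30% uncommon. Cumulative risk at one month cannot exceed that at three months, so the one-month analysis is at least as exposed.

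The size rests on 1:1 allocation, all 75 patients being enrolled and followed, the assumed infection risks and the assumed category frequencies. Two modelling choices lean towards the plan: zip code is omitted, and only the differing variables are entered, although the wording could mean all nine. Adding columns to a model can never remove separation, so entering more variables would not lower the figures.

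**What to change.** In the Aim 2 paragraph of DATA AND SPECIMEN MANAGEMENT, state that the adjusted infection analysis at each time point uses Firth penalized logistic regression with profile-likelihood intervals, or exact logistic regression with exact intervals. Exact regression is practical only with a few discrete covariates, so Firth is the easier default. Add a rule for collapsing sparse levels and keep the number of covariates small.

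The gain from a smaller model can be shown in the forced model described above, with equal education levels and indication split 50:50. Reducing it to training arm plus one binary covariate lowers the share of infinite fits from 49% to 7% at 10% risk, and from 20% to 0.6% at 15%. Firth or exact estimation handles what remains.

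Keep the Chi Square comparison. Optionally add a risk difference with a score or exact 95% confidence interval, which can be reported even when an arm has no infections.

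The cost is a few sentences. The methods are in standard software, and no extra data or patients are needed. The downside is fewer or coarser covariates in the adjusted model.
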